## LIST OF ABBREVIATIONS AND DEFINITION OF TERMS

Abbreviation or Specialist Term	Explanation
AE	Adverse event
ALP	Alkaline phosphatase
ALT	Alanine aminotransferase
ANCOVA	Analysis of covariance
AR (1)	Autoregressive (1)
AST	Aspartate aminotransferase
ATC	Anatomical therapeutic chemical
AUC	Area under the concentration
BMI	Body mass index
BLQ	Below limit of quantification
BIW	Twice per week
C4	7 $\alpha$ -hydroxy-4-cholesten-3-one
CA	Cholic acid
CDCA	Chenodeoxycholic acid
CLDQ	Chronic liver disease questionnaire
CI	Confidence interval
CM	Concomitant medication
CP	Child-Pugh
CV	Coefficient of variation
DB	Double-blind
DBext	Double-blind extension
DCA	Deoxycholic acid
DMC	Data monitoring committee
ECG	Electrocardiogram
eCRF	Electronic case report form
ELF	Enhanced liver fibrosis
EQ-5D-5L	EuroQol five-dimensional
ET	Early termination
EOT	End of treatment
EOS	End of study
FGF-19	Fibroblast growth factor-19

Abbreviation or Specialist Term	Explanation
FXR	Farnesoid X receptor
GGT	Gamma-glutamyl transferase
HA	Hyaluronic acid
HCC	Hepatocellular carcinoma
HCV	Hepatitis C virus
INR	International normalized ratio
IP	Investigational product
ITT	Intent-to-treat
IWRS	Interactive web response system
KM	Kaplan-Meier
LCA	Lithocholic acid
LOESS	Locally estimated scatterplot smoothing
LLOQ	Lower limit of quantification
LLN	Lower limit of normal
LS	Least square
Max	Maximum
MedDRA	Medical Dictionary for Regulatory Activities
MELD	Model of end stage liver disease
Min	Minimum
MMRM	Mixed model repeated measures
MR	Metabolite ratio
OCA	Obeticholic acid (also known as INT-747)
PBC	Primary biliary cholangitis (also known as primary biliary cirrhosis)
PD	Pharmacodynamics
PK	Pharmacokinetics
P3NP	procollagen 3 N-terminal peptide
PT	Preferred term
QW	Once per week
REML	Restricted maximum likelihood
SAE	Serious adverse event
SAP	Statistical analysis plan

Abbreviation or Specialist Term	Explanation
SAS	Statistical analysis system
SD	Standard deviation
SE	Standard error
SI	Standard international
SOC	System organ class
SUSAR	Suspected unexpected serious adverse reaction
TE	Transient elastography
TEAE	Treatment-emergent adverse event
TIMP-1	Tissue inhibitor of metalloproteinase
TLF	Table, listing, and figure
UDCA	Ursodeoxycholic acid
ULN	Upper limit of normal
VAS	Visual analogue scale
WHO	World Health Organization

## 1. SCOPE

This statistical analysis plan (SAP) describes the statistical analyses and data presentations planned for protocol 747-401, A Phase 4, Double-Blind, Randomized, Placebo-Controlled Study Evaluating the Pharmacokinetics and Safety of Obeticholic Acid in Patients with Primary Biliary Cholangitis and Moderate to Severe Hepatic Impairment. It provides a detailed description of the strategies, rationales, and statistical techniques to be used to meet the study objectives and additional details to the statistical analyses that were described in the protocol. This SAP will be finalized and signed prior to database lock. Any deviations from the methods specified in this SAP will be documented in the clinical study report (CSR). If additional analyses are required to supplement the planned analyses described in this SAP, they will be identified as *post-hoc* in the CSR.

## 2. STUDY OBJECTIVES AND HYPOTHESES

### 2.1. Study Objectives

#### 2.1.1. Primary Objective

- To evaluate the PK of OCA and its conjugates, glyco-OCA and tauro-OCA, and OCA metabolite glucuronide compared with placebo
- To evaluate the safety and tolerability of OCA treatment compared with placebo

#### 2.1.2. Secondary Objectives

- To evaluate the effect of OCA treatment compared to placebo on:
  - The MELD score and its components
  - CP score and its components
  - Liver biochemistry including total and direct bilirubin, alkaline phosphatase (ALP), and aminotransferases (alanine aminotransferase [ALT], aspartate aminotransferase [AST], and gamma glutamyl transaminase [GGT]), international normalized ratio (INR), creatinine, albumin, platelets
  - Biomarkers of bile acid synthesis and homeostasis including fibroblast growth factor 19 (FGF-19), 7 $\alpha$ -hydroxy-4-cholesten-3-one (C4), and plasma bile acids

#### 2.1.3. Exploratory Objectives

- To evaluate the effect of OCA treatment compared to placebo on:
  - Noninvasive markers of liver fibrosis (Enhanced Liver Fibrosis [ELF]TM score)
  - Noninvasive measurement of liver stiffness (transient elastography [TE])
- To assess the PK/Pharmacodynamic (PD) relationship of OCA with:
  - PK parameters compared to PD parameters and safety and tolerability assessments

- To assess patient reported outcomes (Pruritus Visual Analogue Scale [VAS], PBC-40, EQ 5D-5L, Chronic Liver Disease Questionnaire [CLDQ])
- To assess clinical events consistent with end-stage liver disease
  - Death (all cause)
  - Liver transplant
  - MELD score  $\geq 15$  (for patients with MELD  $\leq 12$  at baseline)
  - Hospitalization (as defined by a stay of 24 hours or greater) for new onset or recurrence of: variceal bleed, hepatic encephalopathy (as defined by a West Haven score of  $\geq 2$ ), spontaneous bacterial peritonitis
  - Uncontrolled ascites (diuretic resistant ascites requiring therapeutic paracentesis at a frequency of at least twice in a month)
  - Hepatocellular carcinoma (HCC)

## 2.2. Hypotheses

The primary objective of this study is to evaluate the PK of OCA and its conjugates, safety and tolerability of OCA compared with placebo. Therefore, there is no formal statistical hypothesis to be tested.

## 3. SUMMARY OF STUDY DESIGN

This is a double-blind, randomized, placebo-controlled study evaluating the PK and safety of OCA in patients with PBC and moderate to severe hepatic impairment. It is a Phase 4 study in regions where OCA has received regulatory approval for PBC; in all other regions, this study is considered Phase 3b.

[figure not shown]
Approximately 50 patients (including at least 20% of patients with CP-C) will be enrolled in the study. Patients will be screened  $\geq 14$  days but not more than 28 days prior to entering the study (Day 1). Patients who meet all eligibility requirements will be randomized in a 1:1 ratio to 1 of 2 treatment groups: placebo or OCA. Randomization will be stratified by CP class. Baseline MELD scores will be monitored on an ongoing basis to ensure adequate distribution of MELD scores.

Patients will receive double-blind treatment for at least 48 weeks. During the 48-week treatment period (ie, Day 1 through Week 48), an initial safety visit will occur at Week 3. After the Week 6 Visit, subsequent clinic visits will occur approximately every 6 weeks for the assessment of safety, tolerability, PK, and PD. Titration may be considered as early as the Week 12 Visit. Fasting PK samples (ie, trough only) will be obtained from all patients on Day 1, Week 6, and Week 36 prior to dose administration. Post-dose serial PK assessments (including a trough sample) will be performed in all patients at Weeks 12, 18, 24, 30, and 48.

Patients who have completed their 48-week double-blind treatment period will continue double-blind treatment until all randomized patients have completed their participation in the 48-week treatment period and the database for that period is locked (approximately 3 years).

All patients will initiate investigational product (IP) once weekly with 5 mg OCA or matching placebo. Titration may be considered as early as the Week 12 Visit. Following visit procedures at Week 12, if the IP is tolerated and laboratory assessments do not indicate a safety concern, the patient may up-titrate to OCA 5 mg twice weekly and may start the higher dose regimen no earlier than 2 days after they took their last dose. Dosing will then occur at least 3 days apart. Every 6 weeks thereafter, based on tolerability assessments, patients can be considered for further up titration as described below. At each titration visit, the patient may start the higher dose regimen no earlier than 2 days after the prior dose. Patients may titrate to a maximum dose of OCA 10 mg twice weekly at least 3 days apart.

**Figure 1: Study Design**

OCA = obeticholic acid, PBC = primary biliary cholangitis

Notes: Initial dose titration of investigational product may be considered as early as the Week 12 Visit, or any study visit thereafter for patients on all dosing regimens, based on tolerability and safety laboratory tests from the previous visit. Subsequent dose titration(s) may occur no earlier than 6 weeks after the previous dose titration and will be based on tolerability.

Patients who complete Week 48 will continue double-blind treatment until all randomized patients have completed their participation in the 48-week treatment period and the database for that period is locked.

**Table 1. Planned OCA or Matching Placebo Dosing Regimen**

	Child-Pugh B and Child-Pugh C (Moderate and Severe Hepatic Impairment)	
	Treatment Group	
	OCA	Placebo
Starting Dose (Day 1)	5 mg once weekly	matching placebo once weekly
Titration 1a	5 mg twice weekly b	matching placebo twice weekly b
Titration 2a	10 mg twice weekly b	matching placebo twice weekly b

a Planned titration regimen is shown; however, the titration of dose and/or frequency is dependent on patient tolerability.

b Dosing per the twice weekly schedule must be at least 3 days apart.

### **3.1. Subject Selection**

This study will be conducted at approximately 50 international study sites with experience in treating patients with PBC with moderate to severe hepatic impairment defined as CP-B and CP-C. Prospective patients will be identified primarily from the hospital and/or physician's database of patients with PBC, or may be referred from other physicians. Patients may self-refer to an Investigator if they become aware of the study through local, national, or international PBC patient societies, forums, or networks. Subject Inclusion and Exclusion criteria can be found in Sections 8.2 and 8.3 of the protocol.

### **3.2. Randomization and Blinding**

This study will be conducted in a double-blind, placebo-controlled manner. Enrolled patients who meet all eligibility requirements will be randomized in a 1:1 ratio to 1 of 2 treatment groups: placebo or OCA based on a predefined randomization code (generated by Sponsor or designee) using an interactive web response system (IWRS), which the Sponsor intends will serve as a computer-based patient registration system at Screening and Day 1.

Randomization will be stratified by CP class (CP-B or CP-C). Baseline MELD scores will be monitored on an ongoing basis to ensure adequate distribution of MELD scores. The IWRS will serve as the IP inventory and management system and may be integrated with the study database.

The Investigator or designee will be required to register the patient in the IWRS and may be prompted to provide patient data necessary to properly randomize and allocate the patient to treatment. A randomization number will be assigned and IP (placebo or OCA) dispensing information will be provided (eg, bottle numbers allocated) while maintaining the study blind.

The sponsors, patients, investigators, and study site staff will be blinded to the patient's treatment allocation during the patient's participation in the double-blind phase of the study.

Treatment assignment for individual patients will be made available to the Investigator for medical emergency use only (such as unblinding which is necessary in order to treat a serious adverse event through the IWRS system). When possible, the Medical Monitor should be consulted in the event that a medical emergency necessitates unblinding (ie, in situations where knowledge of the blinded treatment assignment is necessary for further medical management of the patient). If it is not reasonable to inform the Medical Monitor in advance of the unblinding, the Investigator must promptly document in the patient's record the rationale for unblinding and should subsequently contact the Medical Monitor to explain any premature unblinding of treatment assignment. Procedures for unblinding a patient's treatment will be provided separately to the Investigator. Similarly, if the Medical Monitor breaks the blind for an individual patient for the purpose of evaluating an emergent safety issue, the Medical Monitor will document within study documentation the rationale, circumstances, and the person or persons being informed about the unblinding.

The data monitoring committee (DMC) will have access to the IWRS and will be able to unblind individual patients. Refer to Section 15.8 of the study protocol for further details regarding DMC access to blinded and unblinded data. The DMC will document details about any unblinded patient data reviews in the closed session DMC minutes, which will be made available

to the Sponsor only after the database is locked and the study is unblinded. Cases of premature unblinding, as noted above, will also be reviewed by the DMC.

Access to treatment assignments will also be made available to the designated Intercept staff responsible for expedited safety reporting of suspected unexpected serious adverse reactions (SUSARs) to the Regulatory Authorities.

### **3.3. Sample Size Determination**

To reasonably characterize the PK of OCA in patients with hepatic impairment, a simulation-based approach estimated a requirement of approximately 20 patients in the OCA treatment group assuming a 15% discontinuation rate. A total of 30 patients is adequate with 10 patients on placebo to be included as a comparator and 20 patients on OCA. An additional 20 patients will be enrolled to support safety and efficacy evaluations. Therefore, approximately 50 patients (including at least 20% of patients with CP-C) will be randomized in a 1:1 ratio to 1 of 2 treatment groups: placebo and OCA.

## **4. ANALYSIS POPULATIONS AND APPROACHES TO ANALYSIS**

### **4.1. Randomized Population**

The Randomized Population will include all randomized patients.

### **4.2. Intent-to-Treat (ITT) Population**

The Intent-to-Treat (ITT) Population will include all randomized patients who received any amount of IP (OCA or placebo). The ITT Population will be the primary population used for summarizing efficacy and pharmacodynamic analyses assessments. Subjects will be analyzed according to randomized treatment.

### **4.3. Safety Population**

The Safety Population will include all patients who received at least one dose of IP (placebo or OCA). The Safety Population will be the primary population used for safety analyses. Subjects will be analyzed according to treatment actually received.

### **4.4. Pharmacokinetic Population**

The PK Population will include all patients receiving OCA who have adequate concentration-time profiles to characterize OCA and its conjugates and must not have any major protocol deviations that potentially affect exposure levels.

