## 11. PHARMACOKINETIC ANALYSES

PK analyses will be performed using the PK Population (definition in [Section 4.4](#)). PK parameters will be derived using Phoenix WinNonlin version 8.0 or higher. The PK concentrations and parameters will be available for:

- Unconjugated OCA
- Glyco-OCA
- Tauro-OCA
- Total OCA (molar sum of OCA, glyco-OCA, tauro-OCA)
- Metabolite OCA glucuronide

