### 11.1. PK Sampling Schedule

Serial and fasting PK assessments will be performed in all patients participating in the study.

- Pharmacokinetic fasting samples prior to the study medication will be obtained from all patients on Day 1, and at Weeks 6, 12, 18, 24, 30, 36, and 48 prior to dose administration.
- Serial PK assessments will be performed in all patients at Weeks 12, 18, 24, 30, and 48 at 0.5, 0.75, 1, 1.5, 2, 2.5, 3, 4, 5, 6, 7, 8, 9, and 24 hours post-dose.

The Week 6 Visit should occur 3, 4, or 5 days after the Week 6 dose (eg, if the Week 6 dose of IP is taken on a Sunday, the patient should come in for the Week 6 Visit between Wednesday and Friday). This allows for the collection of PK data near the mid-point of the weekly dosing interval (ie, 5 mg once weekly).

Patients will receive a dose of IP with approximately 240 mL of water. Patients should not drink additional water for 1 hour after taking the dose of IP and will remain fasted until after the 1-hour sample is collected. A meal replacement drink will be provided following collection of the 1-, 4-, and 7-hour PK sample. The nutritional information of the meal replacement drink should be submitted to and approved by the Sponsor in advance. No other food or drink (water is permitted) will be allowed until after the 9-hour sample collection.

The acceptable windows for the PK blood collection time points are listed in [Table 3](#). However, because the planned non-compartmental PK analyses will use actual collection times (ie, not nominal times), data from samples collected outside of these time windows will still be included in the non-compartmental analyses. PK samples that have a collection time outside the acceptable time window will be considered as “missing” for the calculation of drug concentration summary statistics at that nominal time point.

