## 11.3. Handling of Missing Data, BLQ Data, or Data Exclusions

Missing concentration data for all patients who are administered scheduled study treatments will be considered as non-informative missing and will not be imputed. No concentration estimates will be provided for missing sample values.

For all analyses (drug concentrations and PK parameters), the following rules will apply:

- Concentration values below the assay's lower limit of quantification (BLQ) will be imputed to zero
- The sampling time of pre-dose samples relative to dosing will also be treated as zero

Examples of potential reasons for exclusion of data from PK summary analyses include, but are not limited to:

- Subject not fasted for 8 hours prior to PK visit;
- Subject not adhering to standardized meal timing (or missed meal) during 24-hour PK profile collection;
- Non-standard dosing (eg, drug holiday, altered dose level, altered dose frequency) used prior to PK visit.

Data excluded based on this review will be included in listing outputs but will be excluded from summary tables.

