### 11.5.2. PK Parameters Summarization

PK parameters will be summarized by analyte (unconjugated OCA, glyco-OCA, tauro-OCA, total OCA, and OCA glucuronide), PK parameter, baseline CP category (CP-B, CP-C, and Combined), dosing regimen, and study visit (Week 12, Week 18, Week 24, Week 30, Week 48, and All Visits). For the ‘All Visits’ summary, which summarizes across all visits for each dosing regimen, if a subject has data from multiple visits on a particular dosing regimen, the mean of the values across those visits will be used so that each subject is only represented once. The summary statistics to be used for each PK parameter are described in Table 5 .

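### The PK Population removes a whole patient for any major exposure-affecting deviation, with no time limit, so a deviation confined to one period also discards that patient's unaffected serial profiles

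*SAP*

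**What the plan says.** Section 4.4 sets two conditions for the PK Population. The first concerns data: "The PK Population will include all patients receiving OCA who have adequate concentration-time profiles". The second concerns conduct: the patient "must not have any major protocol deviations that potentially affect exposure levels". Both are properties of a patient. The second names no visit, no period and no option to remove only the affected profile.

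The definition governs everything downstream. Section 11 states that "PK analyses will be performed using the PK Population", and Section 11.5.1 lists individual PK parameters for that population only.

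The rest of the PK plan works below patient level:

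- Section 11.1: "Serial PK assessments will be performed in all patients at Weeks 12, 18, 24, 30, and 48".
- Section 11.3 gives example reasons for leaving data out of the PK summaries, each tied to a PK visit or profile. They include "Subject not fasted for 8 hours prior to PK visit" and "Non-standard dosing (eg, drug holiday, altered dose level, altered dose frequency) used prior to PK visit". Data excluded this way stay in the listings.
- Section 11.5.2 summarises by visit and dosing regimen. For the all-visits row, "if a subject has data from multiple visits on a particular dosing regimen, the mean of the values across those visits will be used".

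Section 3.3 plans "approximately 20 patients in the OCA treatment group assuming a 15% discontinuation rate", within a total of about 50 randomised 1:1, at least 20% of them Child-Pugh C.

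**The concern.** PK is a primary objective and the data are repeated profiles. A major deviation around Week 30 cannot have altered the profiles taken at Weeks 12, 18 and 24. Followed as written, Section 4.4 still removes them, and they leave the parameter listing as well as the summaries.

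Nothing elsewhere in the plan needs a whole-patient rule. The by-visit summaries tolerate different patient numbers at each visit, and the all-visits average uses whatever visits a patient has on a regimen.

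The plan also does not say which section governs when one event is both a major exposure-affecting deviation (4.4) and an example reason under 11.3. The outcomes differ: under 11.3 one visit's data are dropped and stay listed, while under 4.4 the patient goes.

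The Child-Pugh C patients have least to spare, because their few profiles are divided further by regimen and visit.

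**Working it through.** **The plan's own figures.** 20 + 10 + 20 = 50 patients; 1:1 allocation gives 50 / 2 = 25 on OCA. At the 20% minimum, 25 × 0.20 = 5 of these are Child-Pugh C. With 15% discontinuation, 20 × 0.85 = 17 and 25 × 0.85 = 21.25. The requirement of about 20 comes from a simulation whose inputs are not given in the SAP, so it cannot be reproduced. The point does not depend on it.

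**What one event costs under each rule.** Take a patient with all five serial profiles and a major deviation affecting one of them.

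| Rule | Affected profiles removed | Unaffected profiles removed |
|---|---|---|
| Patient level (4.4 as written) | 1 | 4 |
| Profile level (the unit used in 11.3) | 1 | 0 |

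This follows from the wording alone.

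**Illustration across patients.** Let a share q of patients have exactly one affected profile and the rest none. Both q and this pattern are assumptions. With n patients of five profiles each:

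- valid profiles = 5n − qn
- valid profiles lost under 4.4 = 4qn
- share of valid profiles lost = 4q / (5 − q), which does not depend on n

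With n = 21.25 (5n = 106.25 profiles):

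| q (assumed) | Patients removed | Valid profiles lost | Share of valid profiles |
|---|---|---|---|
| 5% | 1.06 | 4.2 of 105.2 | 4.0% |
| 10% | 2.12 | 8.5 of 104.1 | 8.2% |
| 20% | 4.25 | 17.0 of 102.0 | 16.7% |
| 30% | 6.38 | 25.5 of 99.9 | 25.5% |

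Under profile-level exclusion the share of valid profiles lost is zero in every row.

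**Child-Pugh C on OCA.** With 5 patients and 25 scheduled profiles, one such deviation removes 1 / 5 = 20% of the patients and 4 / 24 = 16.7% of the valid profiles.

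**Sections 4.4 and 11.3 side by side.** Section 4.4 defines who is in the population; Section 11.3 removes data within it. The reasons in 11.3 are examples and are not described as major deviations. An unfasted visit can therefore be handled under 11.3 with the patient kept. The sections meet only when the event is also classed as major, and there the plan is silent.

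**Non-standard dosing.** The third example in 11.3 has no look-back limit and leaves the term undefined. In this trial dose level and frequency change by design: note a to Table 1 makes titration depend on tolerability, Appendix A (Dose Regimen) assigns the regimen from up- or down-titration history, and 11.5.2 summarises by regimen. The coherent reading is dosing outside the assigned regimen, but the SAP does not say so.

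**The case against.** The strongest reply is that this is an ordinary two-tier structure: a population definition, then data-level exclusions inside it. Only major deviations trigger 4.4, and Section 5.1 has major deviations identified before database lock and unblinding, which limits choice made with knowledge of treatment. PK is descriptive, with no hypothesis test.

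Much of that stands. The two sections do not contradict each other; they overlap without precedence. Early identification guards against biased choice, although 5.1 speaks of efficacy and safety conclusions rather than PK. Neither fact returns the sound profiles that 4.4 removes.

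Three stronger readings are tempting, and the SAP does not support them:

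- *That the rule understates exposure in severe impairment, because patients with dose reductions or interruptions are the ones removed.* Tolerability-driven titration is part of the plan and is not in itself a deviation under 4.4. The text that mentions altered dosing is the 11.3 example, which acts by visit. Nothing in the SAP links deviations to high exposure, so no direction of bias can be claimed.
- *That the PK sample falls below what was planned.* If each of five visits carried an independent 2%, 5% or 10% risk of a major deviation, 1 − (1 − p)^5 = 9.6%, 22.6% or 41.0% of patients would go, leaving 19.2, 16.4 or 12.5 of 21.25. These rates are invented. Clustering within patients would remove fewer patients at the same rate. Discontinued patients may still have usable profiles. And 17 is inferred, not a threshold stated in the plan.
- *That any exposure-affecting deviation removes the patient.* Section 4.4 requires it to be major.

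**Conclusion.** The point holds as a defect in the unit of exclusion. As written, a major deviation that could affect exposure in one period removes all of that patient's PK data from the summaries and the parameter listing, including up to four unaffected serial profiles. The loss per affected patient follows from the text. The total loss does not, because the SAP gives no deviation rate. The figures of about 8% and 17% of valid profiles, at 10% and 20% of patients with one affected profile, are illustrations resting on that assumed pattern and a full five-profile schedule.

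Retention depends on events up to Week 48, so some selection is possible, but neither its size nor its direction can be shown. The change is still worth making before lock, because it keeps primary-objective data in a small trial at little cost.

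**What to change.** 1. **Section 4.4.** Define the PK Population as all patients who received OCA and have at least one profile that meets the AUC0-24h rules in Table 4 and is not excluded under 11.3.
2. **Section 11.3.** Exclude a profile only if a major exposure-affecting deviation was present at that PK visit, or its effect could still be present then. Include deviations that began earlier and continue. A look-back limited to the interval since the previous PK visit would not do: it would keep later profiles taken under a continuing deviation. Keep the patient's other profiles, and make these decisions before unblinding. This also settles which section governs.
3. **Non-standard dosing in 11.3.** State that a titration regimen recorded in the dosing data does not fall under this term and is summarised under the actual regimen, in line with 11.5.2 and Appendix A.

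The cost is SAP wording and a review of each profile instead of each patient. Patient numbers will differ by visit, so each summary should show its own n; Table 5 already reports n.
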